12.7 Appendix 7. Hepatotoxicity Stopping Rules: Suggested Actions and Follow-up Assessments

Subjects with abnormal hepatic laboratory values (ie, alkaline phosphatase [ALP], aspartate aminotransferase [AST], alanine aminotransferase [ALT], total bilirubin [TBL]) and/or international normalized ratio (INR) and/or signs/symptoms of hepatitis (as described below) may meet the criteria for withholding or permanent discontinuation of Amgen investigational product or other protocol-required therapies, as specified in the [Guidance for Industry Drug-Induced Liver Injury: Premarketing Clinical Evaluation, July 2009](#).

Criteria for Withholding and/or Permanent Discontinuation of Amgen Investigational Product and Other Protocol-required Therapies Due to Potential Hepatotoxicity

The following stopping and/or withholding rules apply to subjects for whom another cause of their changes in liver biomarkers (TBL, INR, and transaminases) has not been identified.

Important alternative causes for elevated AST/ALT and/or TBL values include, but are not limited to:

- Hepatobiliary tract disease
- Viral hepatitis (eg, hepatitis A/B/C/D/E, Epstein-Barr Virus, cytomegalovirus, herpes simplex virus, varicella, toxoplasmosis, and parvovirus)
- Right sided heart failure, hypotension or any cause of hypoxia to the liver causing ischemia
- Exposure to hepatotoxic agents/drugs or hepatotoxins, including herbal and dietary supplements, plants and mushrooms
- Heritable disorders causing impaired glucuronidation (eg, Gilbert's syndrome, Crigler-Najjar syndrome) and drugs that inhibit bilirubin glucuronidation (eg, indinavir, atazanavir)
- Alpha-one antitrypsin deficiency
- Alcoholic hepatitis
- Autoimmune hepatitis
- Wilson's disease and hemochromatosis
- Nonalcoholic fatty liver disease including steatohepatitis (NASH)
- Non-hepatic causes (eg, rhabdomyolysis, hemolysis)

If investigational product(s) is/are withheld, the subject is to be followed for possible DILI according to recommendations in the last section of this appendix.

Rechallenge may be considered if an alternative cause for impaired liver tests (ALT, AST, ALP) and/or elevated TBL, is discovered and the laboratory abnormalities resolve to normal or baseline (see next section in this appendix).

Table 12-2. Conditions for Withholding and/or Permanent Discontinuation of Amgen Investigational Product and Other Protocol-required Therapies due to Potential Hepatotoxicity

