| Analyte | Temporary Withholding | Permanent Discontinuation |
|---------|--|---|
| TBL | > 3x ULN at any time | > 2x ULN |
| | | OR |
| INR | -- | > 1.5x ULN (for subjects not on anticoagulation therapy) |
| | OR | AND |
| AST/ALT | > 8x ULN at any time > 5x ULN but < 8x ULN for ≥ 2 weeks > 5x ULN but < 8x ULN and unable to adhere to enhanced monitoring schedule > 3x ULN with clinical signs or symptoms that are consistent with hepatitis (such as right upper quadrant pain/tenderness, fever, nausea, vomiting, and jaundice) | In the presence of no important alternative causes for elevated AST/ALT and/or TBL values > 3x ULN (when baseline was < ULN) |
| | OR | |
| ALP | > 8x ULN at any time | -- |

ALP = alkaline phosphatase; ALT = alanine aminotransferase; AST = aspartate aminotransferase;
 INR = international normalized ratio; TBL = total bilirubin; ULN = upper limit of normal

Criteria for Rechallenge of Amgen Investigational Product and Other Protocol-required Therapies After Potential Hepatotoxicity

The decision to rechallenge the subject is to be discussed and agreed upon unanimously by the subject, investigator, and Amgen.

If signs or symptoms recur with rechallenge, then Amgen investigational product is to be permanently discontinued. Subjects who clearly meet the criteria for permanent discontinuation (as described in [Table 12-2](#)) are never to be rechallenged.

Drug-induced Liver Injury Reporting and Additional Assessments

Reporting

To facilitate appropriate monitoring for signals of DILI, cases of concurrent AST or ALT and TBL and/or INR elevation, according to the criteria specified in the above, require the following:

- The event is to be reported to Amgen as a serious adverse event within 24 hours of discovery or notification of the event (ie, before additional etiologic investigations have been concluded)
- The appropriate CRF (eg, Event CRF) that captures information necessary to facilitate the evaluation of treatment-emergent liver abnormalities is to be completed and sent to Amgen

Other events of hepatotoxicity and potential DILI are to be reported as serious adverse events if they meet the criteria for a serious adverse event defined in [Appendix 4](#).

Additional Clinical Assessments and Observation

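### Table 12-2's only combined liver criterion (AST/ALT with TBL or INR) is limited to baseline AST/ALT below ULN, so raised-baseline subjects have no permanent-stop criterion and, in part of the range, no withholding criterion

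*Protocol*

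**What the plan says.** Protocol Appendix 7 (Section 12.7) opens with its scope: "The following stopping and/or withholding rules apply to subjects for whom another cause of their changes in liver biomarkers" has not been identified. Table 12-2 then gives two columns.

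- **Permanent discontinuation.** TBL above 2x ULN or INR above 1.5x ULN (if not anticoagulated), together with the AST/ALT cell: "In the presence of no important alternative causes for elevated AST/ALT and/or TBL values > 3x ULN (when baseline was < ULN".
- **Temporary withholding.** Any one of the following: TBL above 3x ULN; AST/ALT above 8x ULN; AST/ALT "> 5x ULN but < 8x ULN for ≥ 2 weeks", or in that band when enhanced monitoring cannot be followed; AST/ALT above 3x ULN with signs or symptoms of hepatitis; ALP above 8x ULN. The INR cell is empty.

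Later in the same appendix, close observation is required for AST/ALT above 3x ULN, or for a 2-fold rise in subjects whose values were already elevated before drug. The authors therefore foresaw raised baselines, but adapted only the observation rule to them.

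AST, ALT and total bilirubin are on the laboratory list (Appendix 2, Table 12-1) and are scheduled at screening only (Section 2.2, Table 2-1). Eligibility sets no numeric AST/ALT limit. Exclusion 217 covers known hepatic dysfunction that may interfere with the study, which is a matter of judgement.

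**The concern.** A joint rise in transaminase and bilirubin or INR with no other explanation is the pattern the permanent-stop column is built for. The baseline condition removes that column for subjects who enter with AST and ALT at or above ULN, and nothing replaces it. Followed as written, the table gives the weaker instruction to the subjects with the worse starting liver tests. At stake is continued dosing, on the table's own terms, through a combined rise that would end treatment in a subject with a normal baseline.

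**Working it through.** The plan gives no figure to reproduce here, so the check applies each cell of Table 12-2 to set values. All values are multiples of ULN and *b* is baseline AST/ALT.

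**Rules as coded**

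- Permanent stop: (TBL > 2 or INR > 1.5) and AST/ALT > 3 and *b* < 1.
- Withhold: TBL > 3; or AST/ALT > 8; or 5 < AST/ALT < 8 with (at least 2 weeks or unable to follow monitoring); or AST/ALT > 3 with hepatitis signs or symptoms; or ALP > 8.

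**Assumptions:** no alternative cause, no symptoms, INR normal unless stated, ALP at most 8x, enhanced monitoring followed, and both enzymes on the same side of ULN at baseline.

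| AST/ALT, TBL | *b* = 0.9 | *b* ≥ 1.0, single sample | *b* ≥ 1.0, lasting 2 weeks |
|---|---|---|---|
| 3.5, 2.2 | stop | neither | neither |
| 4.0, 2.5 | stop | neither | neither |
| 4.9, 2.9 | stop | neither | neither |
| 6, 2.5 | stop | neither | withhold |
| 7.5, 2.5 | stop | neither | withhold |
| 10, 2.5 | stop | withhold | withhold |
| 4, 4 | stop | withhold | withhold |
| 10, 4 | stop | withhold | withhold |

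At *b* = 0.9 the permanent stop applies in 8 of 8. At *b* ≥ 1.0 it applies in 0 of 8. On a single sample, withholding then applies in 3 and neither action in 5; after 2 weeks the split is 5 and 3. The cases were chosen to span the cells, so these counts are not event rates.

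**INR route.** AST/ALT 4x with normal TBL and INR 1.8x is a permanent stop at *b* < 1 and meets no cell at *b* ≥ 1. Because INR has no withholding criterion, a higher INR would not change this.

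**Symptoms.** With hepatitis signs or symptoms, AST/ALT > 3 triggers withholding in 8 of 8 at any baseline.

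**Size of rise.** From *b* = 1.2, AST/ALT 4.0x is a 4.0/1.2 = 3.3-fold rise and 7.5x is a 7.5/1.2 = 6.3-fold rise, so these are not small drifts from a high start. At *b* = 2.5 the picture differs: 3.5/2.5 = 1.4-fold and 4.9/2.5 = 1.96-fold, which a baseline-relative rule would not stop either.

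**Proposed criterion.** AST/ALT > 3 and at least 2 × *b* when *b* ≥ 1, so the threshold is max(3, 2*b*).

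| *b* | 1.0 | 1.2 | 1.5 | 2.0 | 2.5 |
|---|---|---|---|---|---|
| Threshold (x ULN) | 3 | 3 | 3 | 4 | 5 |
| Stops among the 8 cases | 8 | 8 | 8 | 7 | 4 |

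The threshold never falls below the 3x used for a normal baseline, and it rises with baseline.

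**The case against.** The strongest reply is that this is a deliberate choice. The appendix names subjects with elevated pre-drug values and assigns them close observation, and a bare 3x ULN rule suits a raised baseline poorly, as the *b* = 2.5 cases show. Intent cannot be judged from the documents, and the second part stands. It argues for a baseline-relative threshold, however, rather than for none.

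Several other points stand and shrink the problem.

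- Post-screening results come only from unscheduled tests. If hepatitis signs or symptoms prompt the test, withholding already applies.
- In the 5x to 8x band, the longest wait before withholding is 2 weeks (14 of 57 treatment days, 25%). That is a theoretical maximum: TBL above 2x ULN requires retesting every 24 hours until improvement, failure to keep up monitoring triggers withholding, and Section 7.4.2.1 lets the investigator stop drug at any time.
- The table does not say whether the baseline condition is read per enzyme. If it is, a subject with raised ALT but normal AST at baseline still meets the stop once AST passes 3x ULN with TBL above 2x ULN.
- The listed alternative causes include "Right sided heart failure, hypotension or any cause of hypoxia to the liver causing ischemia", plausible in subjects with LVEF of 35% or less, so many rises may fall outside the rules altogether.
- The appendix title presents its content as suggested actions, so even the normal-baseline stop is less absolute than the table alone implies.

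Close observation and discretion do not close the gap entirely. The observation rule orders tests and a search for causes, not an interruption of dosing. Discretion exists equally for normal-baseline subjects, for whom the sponsor still wrote a stopping criterion.

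**Conclusion.** The gap is real and narrow. A subject whose AST and ALT were both at or above ULN at baseline (or any raised-baseline subject, if the condition is not read per enzyme) has no permanent-stop criterion for an unexplained combined rise. If asymptomatic with TBL at most 3x ULN and ALP at most 8x ULN, that subject also meets no withholding criterion at AST/ALT above 3x to 5x ULN, nor above 5x to below 8x ULN for under 2 weeks with monitoring followed. This is a low-priority safety wording change with no bearing on the heart-rate analysis. The number of subjects affected cannot be estimated from the documents.

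Three stronger readings might be inferred and are not supported.

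- *Such subjects are unprotected.* They are not: repeat tests are due within 24 hours, a search for causes is required, and withholding applies at the higher levels or with symptoms.
- *They may be freely rechallenged.* The appendix says "Rechallenge may be considered if an alternative cause for impaired liver tests (ALT, AST, ALP) and/or elevated TBL, is discovered" and the abnormalities resolve, and adds: "The decision to rechallenge the subject is to be discussed and agreed upon unanimously by the subject, investigator" and the sponsor. Only the absolute bar on rechallenge is missing.
- *Their cases escape the 24-hour serious adverse event report.* The Reporting text says "cases of concurrent AST or ALT and TBL and/or INR elevation, according to the criteria specified in the above, require the following". Whether that reaches raised baselines is unclear, so neither answer can be asserted.

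**What to change.** In Table 12-2, in the AST/ALT cell that combines with TBL above 2x ULN or INR above 1.5x ULN, keep the present wording and add, per enzyme: or > 3x ULN and at least 2 times baseline (when baseline was ≥ ULN). Keep the no-alternative-cause condition. The sponsor should confirm the 2-fold multiple, since the appendix now uses it only to start observation.

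If the sponsor does not want an irrevocable stop for these subjects, it should at minimum list the same combination as a temporary-withholding criterion.

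The change needs no new visits, tests or subjects, because baseline AST, ALT and TBL are already taken at screening. The downside is that a few more subjects could stop or interrupt drug, and under the permanent-stop version they could never be rechallenged.

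Clarifying the Reporting sentence is optional and separate. If it is done, it should use laboratory thresholds alone: the report is due "before additional etiologic investigations have been concluded", so it should not depend on the no-alternative-cause condition. Concurrent elevations at withholding level should stay reportable.

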12.8 Appendix 8. Six Minute Walk Test Instructions

Six Minute Walk Test (6MWT) instructions

Set up

Ideally the test should be conducted on a straight 30 metre track¹. If the track needs to be adapted or shortened due to lack of space, ensure that the patient walks the same course on each re-test.

Suggested Equipment:

- [6MWT recording form](#)
- [Rate of perceived exertion - Borg scale](#)
- Pulse oximeter with appropriate sensor
- Stop watch or timer
- Chairs (number will depend on patient's condition and risk)
- Sphygmomanometer and stethoscope, or similar method of accurately assessing BP
- Trundle wheel for measuring the 6MWT track and the distance walked
- Clip board and recording sheet
- Portable oxygen if required

Repeat measures

Two 6MWTs are often recommended for initial assessments due to a learning effect when performing the test. Recent studies have demonstrated however that a single measure is often acceptable^{2,3}.

Should you choose to do repeat measures in succession, this should be done each time so that measures are consistent and a duration of at least 15 minutes provided between tests to allow adequate recovery.

Administering test

1. Prior to walking say to patient:

The object of this test is to walk as FAR AS POSSIBLE for 6 minutes. You will walk back and forth along this course (demonstrate one lap) for six minutes.

You may slow down if necessary. If you stop, I want you to continue to walk again as soon as possible.

You will be informed of the time and encouraged each minute.

Please do not talk during the test unless you have a problem or I ask you a question. You must let know if you have any chest pain or dizziness.

When six minutes is up I will ask you to STOP where you are. Do you have any questions?

2. To begin say to patient:

Start now, or whenever you are ready (start stopwatch when walking starts).

3. During the test:

Provide the following standard encouragements in even tones. Do not use other words of encouragement or body language to speed up.

- At 1 minute: *You are doing well. You have 5 minutes to go.*
- At 2nd minute: *Keep up the good work. You have 4 minutes to go.*
- At 3rd minute: *You are doing well. You are halfway done.*
- At 4th minute: *Keep up the good work. You have only 2 minutes left.*
- At 5th minute: *You are doing well. You have only 1 minute to go.*
- At 6th minute: *Please stop where you are.*

If the patient stops during the test:

Allow the patient to rest or sit in a chair if they wish, and check SpO₂ and heart rate. Ask the patient why they stopped.

Keep the stopwatch running and advise: *Please resume walking whenever you feel able.*

Six Minute Walk Test (6MWT) instructions

Set up

Ideally the test should be conducted on a straight 30 metre track¹. If the track needs to be adapted or shortened due to lack of space, ensure that the patient walks the same course on each re-test.

Suggested Equipment:

- [6MWT recording form](#)
- [Rate of perceived exertion - Borg scale](#)
- Pulse oximeter with appropriate sensor
- Stop watch or timer
- Chairs (number will depend on patient's condition and risk)
- Sphygmomanometer and stethoscope, or similar method of accurately assessing BP
- Trundle wheel for measuring the 6MWT track and the distance walked
- Clip board and recording sheet
- Portable oxygen if required

Repeat measures

Two 6MWTs are often recommended for initial assessments due to a learning effect when performing the test. Recent studies have demonstrated however that a single measure is often acceptable^{2,3}.

Should you choose to do repeat measures in succession, this should be done each time so that measures are consistent and a duration of at least 15 minutes provided between tests to allow adequate recovery.

Administering test

1. Prior to walking say to patient:

The object of this test is to walk as FAR AS POSSIBLE for 6 minutes. You will walk back and forth along this course (demonstrate one lap) for six minutes.

You may slow down if necessary. If you stop, I want you to continue to walk again as soon as possible.

You will be informed of the time and encouraged each minute.

Please do not talk during the test unless you have a problem or I ask you a question. You must let know if you have any chest pain or dizziness.

When six minutes is up I will ask you to STOP where you are. Do you have any questions?

2. To begin say to patient:

Start now, or whenever you are ready (start stopwatch when walking starts).

3. During the test:

Provide the following standard encouragements in even tones. Do not use other words of encouragement or body language to speed up.

- At 1 minute: *You are doing well. You have 5 minutes to go.*
- At 2nd minute: *Keep up the good work. You have 4 minutes to go.*
- At 3rd minute: *You are doing well. You are halfway done.*
- At 4th minute: *Keep up the good work. You have only 2 minutes left.*
- At 5th minute: *You are doing well. You have only 1 minute to go.*
- At 6th minute: *Please stop where you are.*

If the patient stops during the test:

Allow the patient to rest or sit in a chair if they wish, and check SpO₂ and heart rate. Ask the patient why they stopped.

Keep the stopwatch running and advise: *Please resume walking whenever you feel able.*

12.9 Appendix 9. Six Minute Walk Test Recording Form

(Affix patient label here)

Patient ID: _____

Family name: _____

Given name(s): _____

Date of birth: _____ Sex: M F I

Six Minute Walk Test (6MWT) recording form

- Medical history checked
 - Medical clearance provided for the patient to participate in exercise testing
- Contraindications to 6MWT:**
- Resting heart rate > 120 beats / min after 10 minutes rest (relative contraindication)
 - Systolic blood pressure > 180 mm Hg +/- diastolic blood pressure > 100 mm Hg (relative contraindication)
 - Resting SpO2 < 85% on room air or on prescribed level of supplemental oxygen
 - Physical disability preventing safe performance
 - No contraindications identified

| 6MWT 1 | | | | | | Date: | Time: |
|---|----|------|----|-----|-----------------|---|-------|
| Supplemental Oxygen | | | | | | Mobility Aid | |
| Time mins | BP | SpO2 | HR | RPE | Distance walked | Rests / comments | |
| Rest | | | | | | | |
| 1 | | | | | | | |
| 2 | | | | | | | |
| 3 | | | | | | | |
| 4 | | | | | | | |
| 5 | | | | | | | |
| 6 | | | | | | | |
| Recovery 1 | | | | | | | |
| 2 | | | | | | | |
| Total distance: _____ Symptom recovery: _____ HR recovery: _____ Limiting factor: _____ Was test terminated?  No  Yes If yes: when? _____ | | | | | | | |
| 6MWT Termination Criteria:  Chest pain or angina-like symptoms  Heart rate > Predicted HR max.  Evolving mental confusion, light-headedness or incoordination  Physical or verbal severe fatigue | | | | | |  Intolerable dyspnoea, unrelieved by rest  Persistent SpO2 <85% (Note: pending clinical presentation)  Abnormal gait pattern (leg cramps, staggering, ataxia)  Other clinically warranted reason | |

(Affix patient label here)

Patient ID: _____

Family name: _____

Given name(s): _____

Date of birth: _____ Sex: M F I

Six Minute Walk Test (6MWT) recording form

- Medical history checked
 - Medical clearance provided for the patient to participate in exercise testing
- Contraindications to 6MWT:**
- Resting heart rate > 120 beats / min after 10 minutes rest (relative contraindication)
 - Systolic blood pressure > 180 mm Hg +/- diastolic blood pressure > 100 mm Hg (relative contraindication)
 - Resting SpO2 < 85% on room air or on prescribed level of supplemental oxygen
 - Physical disability preventing safe performance
 - No contraindications identified

| 6MWT 2 | | | | | | Date: | Time: |
|---|----|------|----|-----|-----------------|---|-------|
| Supplemental Oxygen | | | | | | Mobility Aid | |
| Time mins | BP | SpO2 | HR | RPE | Distance walked | Rests / comments | |
| Rest | | | | | | | |
| 1 | | | | | | | |
| 2 | | | | | | | |
| 3 | | | | | | | |
| 4 | | | | | | | |
| 5 | | | | | | | |
| 6 | | | | | | | |
| Recovery 1 | | | | | | | |
| 2 | | | | | | | |
| Total distance: _____ Symptom recovery: _____ HR recovery: _____ | | | | | | | |
| Limiting factor: _____ | | | | | | | |
| Was test terminated?  No  Yes If yes: when? | | | | | | | |
| 6MWT Termination Criteria:  Chest pain or angina-like symptoms  Heart rate > Predicted HR max.  Evolving mental confusion, light-headedness or incoordination  Physical or verbal severe fatigue | | | | | |  Intolerable dyspnoea, unrelieved by rest  Persistent SpO2 <85% (Note: pending clinical presentation)  Abnormal gait pattern (leg cramps, staggering, ataxia)  Other clinically warranted reason | |

Amendment 2

Protocol Title: Open-label, Single-arm Study Assessing the Efficacy and Safety of Ivabradine (Corlanor) in African-American/Black Subjects With Heart Failure and Left Ventricular Systolic Dysfunction

Amgen Protocol Number Ivabradine 20160231

Amendment Date: 14 February 2019

Rationale:

This protocol is being amended to:

- 

Description of Changes

Section: Global

Change: Updated document date to **14 February 2019**.

Section: Global

Change: Editorial changes (including typographical, grammatical, and formatting) have been made throughout the document.

Section: Title Page, Key Sponsor Contact

Replace:

| | |
|-------------------|---|
| Name: | [REDACTED] |
| Address: | [name] |
| Telephone Number: | [REDACTED] |
| Email Address: | [REDACTED] |

With:

| | |
|-------------------|---|
| Name: | [REDACTED] |
| Address: | [name] |
| Telephone Number: | [REDACTED] |
| Email Address: | [REDACTED] |

Section: Title Page

Add:

Amendment 2 14 February 2019

Section: 1 Protocol Synopsis, Rationale

Delete:

The goal of this study is to determine the impact of adding ivabradine therapy to the standard of care (SOC) in African-American/Black subjects with HF and reduced ejection fraction (HFrEF) on changes in heart rate (HR) from baseline (SOC alone). Changes in HR from baseline will be correlated with [REDACTED], as well as with the changes from [REDACTED]

baseline in activity level of the subjects, as measured by both a standard 6-minute walk distance and an accelerometer device.

Section: 3.1 Study Rationale

Delete:

Changes in HR from baseline will be correlated with [REDACTED], as well as with the changes from baseline in activity level of the subjects, as measured by both a standard 6-minute walk distance and an accelerometer device.

Section: 4.1 Objectives and Endpoints, Exploratory Endpoints

Delete:

| Exploratory |
|-------------|
| [REDACTED] |

Section: 5.1 Overall Design, Paragraph 4

Delete:

[REDACTED]

[figure not shown]
Section: 9.2.1.3 Medical History

Delete:

The Investigator or designee will collect targeted medical cardiovascular disease history, genetic history (if available), along with the functional NYHA class history that started within 5 years prior to enrollment through screening.

[figure not shown]
Section: 10.4.2.2.3 Exploratory Endpoints, Paragraph 1, Bullets 4-5

Delete:

Section: 10.4.2.2.3 Exploratory Endpoints, Paragraph 3

Delete:

Section: 10.4.2.4 Other Analyses

Delete:

~~10.4.2.4 Other Analyses~~

~~The exploratory endpoints will be summarized descriptively.~~

Section: Appendix 1, List of Abbreviations and Definitions of Terms

Add:

| Abbreviation or Term | Definition/Explanation |
|----------------------|-----------------------------------|
| EDC | electronic data collection |

Section: Appendix 3, Data Quality Assurance, Paragraph 10

Delete:

~~Amgen (or designee) will perform Self-Evident Corrections (SEC) to obvious data errors in the clinical trial database. SECs will be documented in the CRF Standard Instructions and the CRF Specific Instructions, both of these will be available through the electronic data capture (EDC) system. Examples of obvious data errors that may be corrected by Amgen (or designee) include deletion of obvious duplicate data (ie, the same results sent twice with the same date with different visit) and updating a specific response if the confirming datum is provided in the "other, specify" field (eg, for race, reason for ending study).~~

Amendment 1

Protocol Title: Open-label, Single-arm Study Assessing the Efficacy and Safety of Ivabradine (Corlanor) in African-American/Black Subjects With Heart Failure and Left Ventricular Systolic Dysfunction

Amgen Protocol Number 20160231

Amendment Date: 02 April 2018

Rationale:

This protocol is being amended to:

- Change the secondary objective to an exploratory objective
- Clarify that the study will be conducted at 1 to 3 sites
- Clarify that between 30 to 100 subjects will be enrolled in the study
- Update informed consent inclusion criteria
- Clarify genetic background will be collected for a subset of subjects in the studied population
- Update the Schedule of Activities table to clarify that 12-lead electrocardiogram will be collected during screening
- Clarify that only urine pregnancy test will be utilized
- Clarify that heart rate will be measured during the 6-minute walk test
- Update the clinical laboratory tests that will be performed during the study
- Align end of study definitions with the protocol template language
- Clarify that a subject's treatment assignment date should be entered on enrollment case report form
- Recategorize the accelerometer as a medical device (instead of "other treatment procedure") per protocol template instructions
- Correct typographical and formatting errors throughout the document

Description of Changes:

Section: Global

Change: Replace the date 18 May 2017 to **02 April 2018**

Section: Global

Change: Make administrative updates and editorial corrections (including typographical, grammatical, and formatting errors) throughout the document.

Section: Global (Title)

Delete:

Open-label, Single-arm, ~~Single-Center~~ Study Assessing the Efficacy and Safety of Ivabradine (Corlanor) in African-American/Black Subjects With Heart Failure and Left Ventricular Systolic Dysfunction

Section: Title Page

Add:

| | | |
|----------------|-------------------------|----------------------|
| Protocol Date: | Document Version | Date |
| | Original | 18 May 2017 |
| | Amendment 1 | 02 April 2018 |

Section: Protocol Synopsis, Rationale

Add:

Changes in HR from baseline will be correlated with the genetic background of **a subset of subjects with available genetic data** in the studied population, as well as with the changes from baseline in activity level of the subjects, as measured by both a standard 6-minute walk distance and an accelerometer device.

Section: Protocol Synopsis, Objective(s)/Endpoint(s), Secondary

Delete:

| Secondary | |
|---|--|
| 
Assess association of proportion of genetic heritage background in African-American/Black subjects with HR lowering | 
Change in HR from baseline to day 57 among African-American/Black subjects associated with proportion of genetic heritage backgroundChange in HR from baseline to day 57 among African-American/Black subjects with 85% proportion of genetic background and African-American/Black subjects with < 85% proportion of genetic background |

Section: Protocol Synopsis, Overall Design

Delete:

This study is a prospective, ~~single site~~, open-label, single-arm intervention study in African-American/Black subjects with HFREF nested in the Henry Ford Heart Failure Pharmacogenomics Registry, and will be conducted at the Henry Ford Health System in Detroit, MI.

Section: Protocol Synopsis, Number of Subjects

Add:

Approximately **30 to 100 subjects**

Section: Protocol Synopsis, Treatments

Add:

The starting dose of ivabradine is 5 mg twice daily (BID). In subjects with a history of conduction defects, or in subjects in whom bradycardia could lead to hemodynamic compromise, therapy is to be initiated at 2.5 mg BID **based on investigator discretion**.

Section: Protocol Synopsis, Statistical Considerations, Paragraph 1

Delete:

This primary analysis will evaluate the effect of ivabradine on HR reduction at day 57 in African-American/Black subjects overall (the primary endpoint) ~~as well as within each genetic background (secondary endpoints)~~.

Section: Protocol Synopsis, Statistical Considerations, Paragraph 4

Delete:

Efficacy analyses of the primary endpoint will test whether the mean reduction with ivabradine exceeds 5 bpm, ~~which is the reduction that would be assumed with placebo.~~ Summary statistics and least-square means along with 95% confidence interval, analyzed by the repeated-measures linear model, will be provided for the primary endpoint. ~~Correlation analyses will be provided between HR reduction and genetic background as determined by the proportion of African-American heritage (1 of the secondary endpoints).~~ Summary statistics and least square means along with 95% confidence interval, based on the repeated measures linear model, will be summarized for the subgroups based on the proportion of African-American heritage with 85% as the cut-off ~~(the other secondary endpoint).~~

Section: 2.2 Schedule of Activities, Table 2-1 and footnotes

Add:

| Procedure | Screening Period | Treatment Period (Days) | | | | Safety Follow-Up Period/ Early Termination Visit ^a (Phone Contact for Safety Follow-up only) |
|---------------------------|-----------------------|-------------------------|--|--------------------|-----------------------|--|
| | Screening (7 days) | Day 1 ± 2 days | Day 15 ± 2 days (dose titration begins) | Day 29 ± 2 days | Day 57 ± 5 days | Day 87 or 30 days after the last dose of open-label IP |
| 12-lead ECG | X | X | X | | X | |
| 6-Minute walk test (6MWT) | | X | | | X | |

Abbreviations: **6MWT = 6-Minute walk test**; ECG = electrocardiogram; IP = investigational product

Section: 2.2 Schedule of Activities, Table 2-1

Delete:

| Procedure | Screening Period | Treatment Period (Days) | | | | Safety Follow-Up Period/ Early Termination Visit ^a (Phone Contact for Safety Follow-up only) |
|--------------------------------------|-----------------------|-------------------------|--|--------------------|-----------------------|--|
| | Screening (7 days) | Day 1 ± 2 days | Day 15 ± 2 days (dose titration begins) | Day 29 ± 2 days | Day 57 ± 5 days | Day 87 or 30 days after the last dose of open-label IP |
| Investigational product ^h | | X | X | X | X | X ⁱ |

Section: 3.1 Study Rationale

Add:

Changes in HR from baseline will be correlated with the genetic background of **a subset of subjects with available genetic data** in the studied population, as well as with the changes from baseline in activity level of the subjects, as measured by both a standard 6-minute walk distance and an accelerometer device.

Section: 3.2.2 Amgen Investigational Product Background: Ivabradine, Paragraph 3

Replace:

A detailed description of the chemistry, pharmacology, efficacy, and safety of ivabradine is provided in the package insert.

With:

A detailed description of the chemistry, pharmacology, efficacy, and safety of ivabradine is provided in the **Corlanor® (ivabradine) US Prescribing Information**.

[figure not shown]
Section: 4.1 Objectives and Endpoints, Secondary

Delete:

| Secondary | |
|---|--|
| 
Assess association of proportion of genetic heritage background in African-American/Black subjects with HR lowering | 
Change in HR from baseline to day 57 among African-American/Black subjects associated with proportion of genetic heritage backgroundChange in HR from baseline to day 57 among African-American/Black subjects with 85% proportion of genetic background and African-American/Black subjects with < 85% proportion of genetic background |

Section: 4.1 Objectives and Endpoints, Exploratory, Bullet 2

Replace:

[figure not shown]

With:

Section: 4.1 Objectives and Endpoints, Exploratory, Bullet 4

Add:

Section: 4.1 Objectives and Endpoints, Safety

Add:

| | |
|---|---|
| 
• Evaluate the safety and tolerability of ivabradine in African-American/Black subjects with HFrEF | 
• Subject incidence of treatment-emergent adverse events• Vital signs at each scheduled assessment |
|---|---|

Section: 5.1 Overall Design, Paragraph 4

Replace:

A secondary objective will be to correlate the HR response to ivabradine in this population with the proportion of the specific genetic background characteristic of African-American/Black subjects.

With:

An exploratory objective in a 

Section: 5.1 Overall Design, Paragraph 5

Delete:

This study is a prospective, ~~single-site~~, open-label, single-arm intervention study in African-American/Black subjects with HFrEF ~~nested in the Henry Ford Heart Failure Pharmacogenomics Registry, and will be conducted at the Henry Ford Health System in Detroit, MI.~~

Section: 5.1 Overall Design, Paragraph 5

Add:

Approximately **30 to** 100 subjects will be enrolled to receive ivabradine in an open-label design.

Section: 5.1 Overall Design, Paragraph 7

Add:

In subjects with a history of conduction defects, or in subjects in whom bradycardia could lead to hemodynamic compromise, therapy is to be initiated at 2.5 mg BID, **based on investigator discretion.**

Section: 5.2.2 Number of Sites

Replace:

One investigative site in the US will be included in the study.

With:

One **to 3** investigative sites in the US will be included in the study.

Section: 5.3.1 End of Study Definition, Paragraphs 1 and 2

Replace:

Primary Completion: The primary completion date is the same as the end of study date and is the date when the last subject has completed the study (ie, last subject last visit).

With:

Primary Completion: The primary completion date is **defined as the date when the last subject is assessed or receives an intervention for the final collection of data for the primary endpoint(s), for the purposes of conducting the primary analysis, whether the study concluded as planned in the protocol or was terminated early.**

The primary completion date is the date when the last subject has completed the **assessments for day 57**.

Section: 5.3.1 End of Study Definition, Paragraph 4

Replace:

End of Study: The end of study date is defined as the date when the last subject at the site is assessed or receives an intervention for evaluation in the study (ie, last subject last visit).

With:

End of Study: The end of study date is defined as the date when the last subject **across all sites** is assessed or receives an intervention for evaluation in the study (ie, last subject last visit), **following any additional parts in the study (eg, safety follow-up), as applicable**.

Section: 5.4 Justification for Investigational Product Dose

Replace:

Ivabradine will be initiated at 5 mg BID daily dosing (with option to reduce initial dosing to 2.5 mg BID based on investigator discretion), and the dose titration will follow the US package insert, as indicated in Table 5-1.

With:

Ivabradine will be initiated at 5 mg BID daily dosing (with option to reduce initial dosing to 2.5 mg BID based on investigator discretion), and the dose titration will follow the **Corlanor® (ivabradine) US Prescribing Information**, as indicated in Table 5-1.

Section: 6.1 Inclusion Criteria, Criterion 101

Replace:

101 Subject's legally acceptable representative has provided informed consent prior to any study-specific activities/procedures being initiated when the subject has any kind of condition that, in the opinion of the Investigator, may compromise the ability of the subject to give written informed consent.

With:

101 Subject has provided informed consent/**assent** prior to **initiation of** any study-specific activities/procedures.

Section: 7.1.1 Investigational Products, Table 7-1

Replace:

After 14 days, tolerability to be assessed as well as resting HR with dose adjustment, as recommended in the US package insert.

With:

After 14 days, tolerability to be assessed as well as resting HR with dose adjustment, as recommended in the **Corlanor® (ivabradine) US Prescribing Information**.

Section: 7.1.3 Medical Device, Paragraph 3 (moved original language from Section 7.1.5)

Add:

Heart rate (HR) **during the 6MWT** will be measured by an HR monitor at specified time points (see Table 2-1 **for 6MWT schedules**). An accelerometer will also be used throughout the study. Any **adverse** events associated with the accelerometer (eg, allergic reaction to components of the instrument) will be captured **in the Events CRF as a procedure-related event. Data collected from the accelerometer will not be available nor reviewed until after the end of the study (ie, last subject, last visit).**

Section: 7.1.5 Other Treatment Procedures

Replace:

Heart rate (HR) will be measured by an HR monitor at specified time points (see Table 2-1). An accelerometer will also be used throughout the study. Note that the accelerometer is not considered a medical device and is not manufactured by Amgen. Any events associated with the accelerometer (eg, allergic reaction to components of the instrument) will be captured as procedure-related events (see Section 9.2.3.1.1.2).

With:

There are no other treatment procedures in this study.

Section: 7.2 Method of Treatment Assignment, Paragraph 2

Add:

The treatment assignment date is to be documented in the subject's medical record and on the enrollment CRF.

Section: 7.4.2.1 Amgen Investigational Product: Ivabradine

Replace:

Ivabradine will be initiated at a 5 mg BID dosing (with option to reduce initial dosing to 2.5 mg BID based on investigator discretion as per US package insert.

With:

